## 9 SUBJECT RECRUITMENT

### 9.1 Identification of trial participant

Patients who potentially meet the eligibility criteria will be identified by the clinical team or during the regional urology cancer MDT team meetings at participating sites. They will be approached by one of the clinical team initially and then the trial team if they are willing to discuss the trial further.

These potential trial patients will be given the ethics committee approved PIS in the form of a physical copy or by email. The patient must be given sufficient time for consideration (without breaching the NHS cancer treatment times) and given the opportunity to ask questions about the trial before deciding whether or not to participate. The right of the patient to refuse to participate in the trial, with or without giving a reason, must be respected. If they are willing to participate in the trial, they will be asked for their informed consent to participate in this trial. PIC sites can issue a PIS only.

### 9.2 Screening and Consent

After a potential participant has had sufficient time to read the PIS, the enrolment process will follow these steps:

- The purpose of the research and the trial procedure is outlined again to the participant to ensure they understand. If the subject is willing to proceed, the participant will be asked to sign the approved trial consent form. This form may be a hard copy or an electronic consent form sent via an NHS account to the participants email. The original signed consent form will be filed in the investigator site file (ISF) after co-signature by an appropriate member of the research team. A copy will then be given to the participant and a copy filed in the hospital case notes. In the case of an electronic consent form, once signed and sent back to the research team, a fully co-signed copy is sent back to the participant, a copy is printed and stored in the ISF and a copy is stored in the hospital case notes. Please see section 9.3 for further details on e-consent.
- If the participant is willing to take part in the trial, eligibility to enter the trial is assessed based on inclusion and exclusion criteria. If all trial criteria are met, the screening visit CRF is completed. If a participant declines, this is also recorded in the screening log. A unique screening number will be assigned to participants recorded on the screening log.
- The participant is deemed to be recruited into the trial and the participant's GP is informed. At this point a unique subject trial number is allocated.
- Using the Sealed Envelope randomisation system, the patient is randomised using their allocated trial number and will be assigned to either the control or intervention arm. They will then be informed of their date for surgery.

- The patient will be blinded as to which arm they are randomised to. The surgeon will not be blinded. Unblinding will only be performed if an adverse event occurs where knowledge of allocation is perceived by the PI to be important in determining ongoing management.

## 9.3 Alternative consenting procedures due to COVID-19

### 9.3.1 e-consent

In line with the HRA COVID-19 guidance released on 28 May 2020, electronic methods for seeking, confirming and documenting informed consent in research studies can now be designed to minimise patient contact and reduce risk to both patient and healthcare practitioner (<https://www.hra.nhs.uk/covid-19-research/seeking-consent-covid-19-research/>). This has been implemented via an online consent form mimicking that of the currently approved paper copy.

The e-consent form is built using the Research Data Collection Service (REDCap). Owing to the process collecting patient identifiable data the e-consent forms, resides within the REDCap service hosted behind the UCL Data Safe Haven which conforms to NHS Data Security & Protection Toolkit and ISO 27001 Information Security standards (<https://www.ucl.ac.uk/isd/services/file-storage-sharing/data-safe-haven-dsh>).

## 10 TRIAL INTERVENTIONS

### 10.1 Robot-assisted radical prostatectomy (RARP)

Patients will undergo RARP using the DaVinci surgical system as per standard of care in the NHS, and by a surgeon who has performed a minimum of 100 cases.

#### 10.1.1 Control Arm: Standard RARP

Standard RARP (control arm) is performed as per NHS routine practice at participating regional uro-oncology sites. Pre-operative parameters used to guide surgeon Nerve Spare (NS) decision include mpMRI NS planning sheet prepared in conjunction with a consultant genito-urinary radiologist, prostate biopsy tumour histology information and digital rectal examination under general anaesthesia. Individual surgeons are asked after RARP to grade the quality of NS performed on each side numerically as seen below (25):

- Grade 0 - No nerve spare. Wide excision of lateral pelvic fascia (LPF) and Denonvilliers' fascia.
- Grade 1 - Limited nerve spare, or partial/incremental nerve spare. Incision through outer compartment of LPF.
- Grade 2 – Interfascial nerve spare. LPF is taken just outside the layer of the veins of the prostate capsule. Still largely preserving the large neural trunks (also known as the NVBs).
- Grade 3 – Intrafascial nerve spare. LPF is taken just outside the prostate capsule. Represents greatest possible NS.

NeuroSAFE PROOF collects detailed information on histological surgical margin status for safety and future publication purposes. Descriptions of histological diagnosis can differ between sites due to varying interpretations of histological analyses. In line with quality assurance, we will request anonymised pathology reports to ensure accurate, standardised reporting in the trial database. This will occur across both arms of the trial.

#### 10.1.2 Intervention Arm: NeuroSAFE RARP

NeuroSAFE RARP (intervention arm) will be performed in accordance with previously described methods, initially developed at the Martini Clinik, Hamburg, Germany. All patients in the NeuroSAFE arm will undergo initial bilateral NS where technically possible. The procedure differs from standard RARP in that initial insertion of the robotic camera port is through a modified incision using the Alexis Laparoscopic System (Applied Medical, Rancho Santa Margarita, CA).

Once the specimen is disconnected from its attachments, the specimen can be removed from the patient through the protected incision immediately.

Pneumoperitoneum can be re-established quickly by placing the laparoscopic cap back on the Alexis.

The specimen will then be painted by the operating surgeon (sites may differ, but at UCLH; yellow for left and green for right side of the prostate). The painted areas can be sprayed with a fixative spray if site prefers (to prevent ink running). The specimen will be delivered expediently to the pathology laboratory where frozen section analysis of the painted areas will be undertaken. Whilst this analysis is taking place the robot will be re-docked and pneumoperitoneum established. The robotic instruments will be reinserted. The surgeon will proceed to fashion the urethro-vesical anastomosis and perform a pelvic lymphadenectomy (where indicated) whilst the result of the frozen section analysis is awaited.

Upon delivery of the prostate gland to the pathology lab, a sharp blade will be used to remove the pre-painted surface of the gland (which had been in contact with the neurovascular bundles). The tissue sample will be snap frozen and embedded in OCT. Using a cryostat, 10-micron thick slices will be placed on slides. The entire length of the area of interest will be sampled in this way generating an average of 5 frozen sections per side and approximately 10 in total. The slides will be stained with H&E and will be examined by a consultant pathologist. As soon as examination is complete the pathologist will telephone the operating surgeon to give the result. On frozen section analysis, presence of cancer cells at the inked surface margin of the specimen constitutes a positive margin and the length of any positive surgical margin will be recorded.

Detailed results of the frozen section examination will be collected and included in the results, including number of sections positive, length of positive margin, grade of cancer cells seen at the margin, identity, and seniority of pathologist. When the frozen section examination demonstrates cancer at the margin of the prostate as per pathology reporting protocol, secondary resection (SR) of the NVB is performed according to one of two ways on each side\*:

1. No tissue resected  
or
2. Entire neurovascular bundle resected.

\*In the presence of an IFS PSM, the performance of SR of the ipsilateral NVB will be made if any of the following are present:

- (1) any PSM on multiple sections on a side,
- (2) any Gleason grade 4 or grade 5 adenocarcinoma at the margin.
- (3) any single section PSM >2 mm of Gleason Grade Group 1.

If none of the above are present (including up to 2mm of Gleason Grade 3 at the inked margin) no SR will be performed.

Technically during surgery, SR of the ipsilateral NVB is performed in the following way: all tissue from the cut edge of Denonvilliers' fascia medially, the pararectal fat laterally, the pedicle cranially, and just beyond the urethrovesical anastomosis (including the puboprostatic ligament and Walsh's pillar) caudally is removed en

bloc. Secondarily resected tissue is sent for routine paraffin embedded histological analysis and is not analysed as part of the intraoperative frozen section.

Detailed times of the beginning of the RARP, the removal of the prostate for specimen painting, arrival of specimen in laboratory, communication of details of fresh frozen section to the surgical team and finishing the RARP are recorded on the day of surgery.

When recording a secondary resection in the database (if applicable), this will be recorded as either:

- No tissue resected (due to none of the above 3 conditions being present)
- Entire bundle resected (due to 1 or more of the above conditions being met)

If the entire bundle is resected, this will automatically be considered as Grade 0, or non-nerve spare, on the side that SR was performed.

## 10.2 Multiparametric MRI prostate

All patients will have pre-biopsy mpMRI as per the local practice's diagnostic pathway. All radiologists will have at least 2 years of experience in prostate MRI reading. MRI diagnostic tumour detection performance is not formally assessed as all patients enrolling into NeuroSAFE PROOF already have tissue (biopsy) diagnosis of prostate adenocarcinoma and this is not the purpose of the trial. Radiologists are provided with clinical details including PSA, biopsy tumour results, biopsy method, medical history, and any other risk factors such as family history to aid their MRI interpretation. Local tumour staging (according to the PIRADS anatomic division of the prostate at the base, the mid gland and the apex) is graded according to a modified 5 level Likert scale based on the risk scoring system by the European Society of Urological Radiology (ESUR)(26), (1 = No signs of extra-prostatic extension (EPE), 2 = No convincing signs of EPE, 3 = EPE might be present, 4 = EPE is likely, 5 = EPE is highly likely).

Seminal vesicle invasion, lower sphincter invasion, and bladder neck invasion is reported as categorical ancillary reports. Subsequently, the radiologist using the mpMRI makes a NS recommendation for each side of the prostate for each participant regardless of treatment arm allocation. The radiological NS recommendation will be recorded:

- Nerve Sparing: Yes
- Nerve Sparing: No
- Digital rectal examination dependent.

Image-based mpMRI surgical NS planning is aimed to assist surgeons, but NS will still be performed in both control and intervention arm as per the operating surgeon's discretion.

During image based surgical NS planning, all mpMRI scans will be graded as to their quality according to the radiologist who reads the images. Scoring system will be a 1-5 Likert score. Description of criteria on scan required to give a quality score will be based on the following:

1. All three sequences are of insufficient quality to score any lesions.
2. Two out of the three sequences are not diagnostic; therefore, it is not possible to score any lesions.
3. It is possible to score a lesion (rule in) but it is not possible to exclude significant lesions (rule out).
4. One of the sequences is not of sufficient quality. Overall, it is possible to score the lesion (rule in) and rule out lesions in the background.
5. T2, DWI (Diffusion Weighted Imaging) and DCE (Dynamic Contrast Enhanced) are each independently diagnostic quality. The radiologist is able not only to diagnose (rule in) lesions but also to rule out lesions in the background.

### 10.3 Other prostate evaluation technologies and co-enrolment

Prostate tissue or liquid samples pertaining to prostate cancer research of men enrolled in the NeuroSAFE trial can be used for other intraoperative cytopathological prostate evaluation technologies which will not affect clinical care or performance of treatment as described by this protocol (with their consent). Any 'other' margin evaluation technology assessments at participating sites must have the written approval from the TMG. Any additional prostate specific evaluation technologies will be reflected in the patient PIS and consent forms.

Participating sites considering co-enrolment of NeuroSAFE PROOF patients onto other studies must also have written approval from the TMG.

### 10.4 UCLH Biobanking

The NeuroSAFE PROOF team works closely with other Prostate Cancer Research teams, including the Molecular Diagnostics and Therapeutics Group at University College London. We understand the research need for successful collaboration in order to maximise the efficient use of research resources. As such, we will invite participants in the NeuroSAFE PROOF trial to consent to the use of their tissue for further translational cancer biology research such as that described in the PEOPLE study.(35) During cut up for intra-operative analysis, tissue from the prostates of participants will be reserved for collection by the Molecular Diagnostics and Therapeutics Group without compromising the performance of the NeuroSAFE technique, the assessment of the prostate specimen for final histological diagnosis, nor elongating the length of the operation/time a man spends under general anaesthetic. The performance of fresh tissue collection from the prostates of men involved will not influence decisions about their clinical care and will only be used for future scientific research studies. It is proposed that matched tumour and benign

prostate tissue will be sampled and collected for local research projects involving biomarkers, diagnostics, and therapeutics for prostate cancer. Methodology of these investigations will include but not be limited to, ex vivo cultures, genomics, and immunohistochemistry. All samples will be pseudonymised and all data will be stored securely within NHS frameworks. All tissue will be stored and tracked in accordance with the Human Tissue Act, with regular internal audits to ensure sample and data security.

Details of the proposed tissue sampling will be described in the REC approved Participant Information Sheet and will be included as an additional 'opt-in' on the Informed Consent Form. A prospective participant may prefer not to consent to tissue sampling for molecular diagnostics and therapeutics and may still consent to being involved in the NeuroSAFE PROOF trial.

## 11 DATA COLLECTION

Responsibility for data collection will be taken by a nominated individual. Data will be collected in eCRF format. Data will be held according to the Data Protection Act 2018 and the UK General Data Protection Regulation (GDPR). Data will be pseudo-anonymised as necessary. Each participant will be given a trial number, and this will be used on all trial records. This trial number will be known by all NeuroSAFE site staff. All clinical information including scans, biopsy results and blood results will be kept in trial records and analysed at the end of the trial. The records will be kept in a secure manner in the research offices with access available to named individuals from the trial group only. All imaging data will be held confidentially and processed by the named investigators for the purpose of image registration analysis, including the use of secure computer software for video linked proctoring between sites. The paper records will be retained for a minimum of 20 years after the end of the trial, according to the local hospital's guidelines.

### 11.1 Data transfer (handling, processing and storage)

In the trial, demographic data, clinical end points, surgical, pathology and imaging outcomes, and patient reported outcome data from questionnaires will be collected in accordance with the patient consent form, patient information sheet and various sections of this protocol.

The pseudo-anonymised trial data will be appropriately sent to the trial statistician, please see the trial summary for statistician's contact details, for statistical analysis. UCL as the sponsor, will act as the data controller.

Research staff under the supervision of the principal investigator will process, store and dispose of the paper CRFs and data in paper form in accordance with all applicable legal and regulatory requirements, including the Data Protection Act 2018 and any amendments thereto. All patient data will be stored centrally at site in a locked filing cabinet controlled by the principal investigator.

Data entered electronically (e-CRFs) will be stored on secure servers hosted by an approved UCL sub-contractor - AIMES Management Services. AIMES exceed NHS security standards and are:

- Cyber Essentials Accredited
- Health and Social Care Network Access Compliant
- NHS Data Security and Protection Toolkit Compliant (Standards Exceeded)
- ISO27001:2013 Accredited

UCL will remain the data controller.

## 11.2 Video Collection

Video recordings of all NeuroSAFE operations will be anonymised and linked to each patient's unique trial NRS number. These videos will be stored on an encrypted external hard drive at each site in a locked filing cabinet until the end of the trial before being uploaded and stored in UCL's data safe haven. These recordings are collected to allow for quality control review.

## 11.3 Health Economics Analysis

A cost-utility analysis of the NeuroSAFE RARP compared to standard RARP will be undertaken using accepted methods. We will analyse cost-effectiveness using a short-run time horizon of 12 months and 2 years (within the trial period - all participants will be followed for at least 2 years). Costs will be assessed from the perspective of the NHS and PSS. Cost components included in the analysis will be the cost of the intervention (standard RARP and NeuroSAFE RARP); NHS costs (inpatient and outpatient visits, diagnostic tests, medications). Resource use data will be collected retrospectively from patients using questionnaires (resource use diary) at 3 months, 6 months 12 months and 2 years. Unit costs will be taken from standard sources.

The cost-effectiveness measures in the short-term model will be the incremental cost per unit of change in the QALY gained. Costs will be measured as described. QALYs will be calculated based on the health-related quality of life (HRQoL) collected using EQ5D5L and RAND36 questionnaires. Patients' utility profiles will be constructed assuming a straight line between each patient's HRQoL scores at each follow-up point. The QALYs experienced from 3 months to 2 years will be calculated as the area underneath this profile. Cost-effectiveness will be calculated as the mean cost difference between NeuroSAFE RARP versus RARP divided by the mean difference in outcomes (QALYs) to give the incremental cost-effectiveness ratio (ICER). A sensitivity analysis will be performed to control for input parameters uncertainty.

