#### 7.2.2.4. Quality of life

Comparison of the proportion of men's quality of life on NeuroSAFE intervention compared to control arm.

- Analysis of EQ-5D-5L scores to produce QALYs at 12 months by arm
- Analysis of RAND36 scores to produce QALYs at 12 months by arm
- Analysis of EPIC-26 scores to produce QALYs at 36-, 48-, and 60 months and a maximum frequency of annually thereafter by arm

Graphical presentation and descriptive analysis of RAND36 and EQ-5D-5L at 3-, 6-, 12- and 24-months post-surgery.

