3.1 Schedule of assessments

Visit	Screening/ Baseline	Random- isation	Treatment	Visit 2 3 months	Visit 3 6 months	Visit 4 12 months
Informed consent	x					
Randomisation		x				
Fitness for surgery assessment	x					
PSA	x			x	x	x
Standard care referral pathway to regional uro-oncology centre	x					
MRI guided pre-op surgical planning			x			
RARP (standard/control or NeuroSAFE/intervention)			x			
Adverse events			x	x		
EQ-5D-5L – (in clinic)	x			x	x	x
ICIQ – (in clinic)	x			x	x	x
IIEF – (in clinic)	x			x	x	x
RAND36 – (in clinic)	x			x	x	x
Additional Erectile function questionnaire				x	x	x
Adjuvant Treatments Assessment				x	x	x
Health Resource Diaries data collection				x	x	x

The study collected additional data through electronic PROMs, paper PROMs or telephone consultation at 2 years (RAND36, IIEF, EQ-5D-5L, ICIQ and Additional EF questionnaire), and at 3, 4 and 5 years via additional medical record review (EPIC-26, PSA & Adjuvant therapies) and telephone or clinic (BCR rates). These longer-term data are not covered in this SAP.

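### QALYs are counted only from 3 months while costs start with the operation, so the first three months are missing from the ICER denominator

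*Protocol*

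**What the plan says.** Protocol section 11.3 fixes the period of the cost-utility analysis: "We will analyse cost-effectiveness using a short-run time horizon of 12 months and 2 years". It describes the utility curve: "Patients' utility profiles will be constructed assuming a straight line between each patient's HRQoL scores at each follow-up point". Baseline is not named as one of the points. The area is then defined: "The QALYs experienced from 3 months to 2 years will be calculated as the area underneath this profile".

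On the cost side, "Cost components included in the analysis will be the cost of the intervention (standard RARP and NeuroSAFE RARP"), together with NHS costs. "Resource use data will be collected retrospectively from patients using questionnaires (resource use diary) at 3 months, 6 months 12 months and 2 years". The ICER is the mean cost difference "divided by the mean difference in outcomes (QALYs) to give the incremental cost-effectiveness ratio (ICER").

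The table of assessments in protocol section 7.4 marks EQ-5D-5L and RAND36 at screening/baseline and at 3, 6 and 12 months, with the 2-year collection in a combined row. The SAP schedule (section 3.1) also marks both at baseline, the former in the row "EQ-5D-5L – (in clinic"). Protocol section 7.2.2.4 lists "Analysis of EQ-5D-5L scores to produce QALYs at 12 months by arm" without a starting point. SAP sections 1.2.2 and 2.1 leave quality of life and health economics to separate plans, which are not among the documents.

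**The concern.** An ICER is interpretable only if its numerator and denominator cover the same period. Here the cost of surgery, including the frozen-section procedure that distinguishes the arms, is counted at time 0, but effects start to accrue three months later. Nothing in either document justifies the later start or adds the missing segment elsewhere.

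The omitted months are not neutral in this trial. Protocol section 13.7.2 limits observation of serious adverse events to 90 days after the operation, because later events are unlikely to be due to surgery. Section 13.7 expects temporary incontinence in every man, and section 5.1 hypothesises better continence recovery at 3 months with NeuroSAFE. If the arms differ in early recovery or early harm, some of that difference falls in the period that earns no QALYs. A complication that is treated and resolved before 3 months could add cost without any loss of utility being recorded.

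**Working it through.** The documents state no QALY, cost or ICER figure, so there is nothing to reproduce. The check is how much the 3-month start removes.

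**Inputs from protocol sections 11.3 and 7.4.** Utility at t = 0 (baseline), 0.25, 0.5, 1 and 2 years; straight lines between points; area taken from 0.25 years; horizons of 1 and 2 years.

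**Assumptions.** Mean utility is equal between arms at baseline (randomised arms). The between-arm differences d(t) are illustrative, because the documents give none. The baseline score is placed at surgery.

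**Step 1: time omitted.** 3/24 = 12.5% of the 2-year horizon; 3/12 = 25% of the 12-month horizon. Section 11.3 states the 3-month start only for the 2-year area. For 12 months it is inferred from the profile being built on follow-up points.

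**Step 2: QALY difference omitted.** Let g be the utility difference at 3 months. The missing segment is a triangle: 0.5 × 0.25 × g = 0.125g.
- g = 0.02 gives 0.0025 QALYs
- g = 0.05 gives 0.00625
- g = 0.10 gives 0.0125

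**Step 3: constant difference d from 3 months on.**
- 12 months: planned 0.75d; full 0.75d + 0.125d = 0.875d. Share missing 0.125/0.875 = 14.3%.
- 2 years: planned 1.75d; full 1.875d. Share missing 0.125/1.875 = 6.7%.

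For a given cost difference, planned ICER ÷ full-horizon ICER = full increment ÷ planned increment: 0.875/0.75 = 1.17 at 12 months and 1.875/1.75 = 1.07 at 2 years.

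**Step 4: other shapes.**

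| d at 3, 6, 12, 24 months | Horizon | Planned | Omitted | Full | ICER ratio |
|---|---|---|---|---|---|
| 0.04, 0.02, 0, 0 (early gain that fades) | 12 months or 2 years | 0.0125 | 0.0050 | 0.0175 | 1.40 |
| 0, 0.01, 0.02, 0.02 (late gain) | 12 months | 0.00875 | 0 | 0.00875 | 1.00 |
| 0, 0.01, 0.02, 0.02 (late gain) | 2 years | 0.02875 | 0 | 0.02875 | 1.00 |
| −0.02, 0, 0.02, 0.02 (early loss, then gain) | 12 months | 0.0025 | −0.0025 | 0 | full ICER undefined |
| −0.02, 0, 0.02, 0.02 (early loss, then gain) | 2 years | 0.0225 | −0.0025 | 0.0200 | 0.89 |

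In the fading case the omitted share is 0.005/0.0175 = 28.6%.

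**Step 5: role of baseline.** If the arms differ by b at baseline, the first segment becomes 0.5 × 0.25 × (b + g) = 0.125(b + g). Once the baseline score enters the area, a chance imbalance enters the QALY difference directly. That is a reason to adjust for it.

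**The case against.** The strongest reply is that section 11.3 is a summary that promises standard methods, and that the governing health-economic plan has not been seen. That plan may set the right window. This stands as a limit: the documents cannot show that the final ICER will omit the period. It does not remove the point, because the protocol's rule is explicit and would carry over unless someone changes it.

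Second, the 3-month score is already the first point of the planned profile and contributes to the area from 3 to 6 months. An early benefit still present at 3 months is therefore partly counted. This is correct; what is lost is the 0.125g before that point.

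Third, no utility is measured between baseline and 3 months, so a straight line from a pre-operative score would miss a deeper post-operative dip. This also stands. A dip of the same size in both arms would cancel in the difference, but one that differs between arms would not be recovered.

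Four stronger readings are tempting, and the documents do not support them:
- A reader might infer that a quarter of the effect is lost. The 25% is a share of time, applies only to the 12-month horizon, and rests on an inferred start there.
- A reader might infer that the ICER is inflated against NeuroSAFE. The direction depends on g, which is unknown.
- A reader might infer that the late start rules out baseline adjustment. It does not: section 11.3 is silent on adjustment, and baseline utility could be a covariate with either window.
- A reader might infer that all resource use is counted from surgery. Only the operation's cost is clearly at time 0; the recall start of the 3-month diary is not given.

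**Conclusion.** The point holds as a mismatch of periods. Followed as written, section 11.3 sets costs that include the operation against QALYs that begin three months later, although a baseline score is scheduled. This is a rule that needs correcting, not merely a missing detail.

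The size is 0.125g QALYs, given equal baselines and linear interpolation. If the difference is constant from 3 months, the ICER is 1.07 times its full-horizon value at 2 years and 1.17 times at 12 months, the latter if the same start applies. The assumed shapes run from no effect, through 1.40 times for an early gain that fades, to 0.89 times at 2 years for an early loss followed by a gain. These are illustrations, not predictions. Since neither size nor direction is known in advance, the window should be settled before unblinded economic data are analysed. The primary endpoint is unaffected; this concerns a secondary economic outcome.

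**What to change.** Amend protocol section 11.3, and carry the change into the separate health-economic plan, so that:
- each patient's utility profile starts at the baseline EQ-5D-5L (or RAND36) score, placed at the date of surgery, and runs in straight lines through the follow-up scores;
- QALYs are the area from surgery to 12 months and from surgery to 2 years, with both start points stated;
- the between-arm QALY difference is estimated with baseline utility as a covariate, in line with the baseline adjustment in SAP sections 4.7 and 4.8.

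The same text should say from what date the 3-month resource diary asks patients to report, so that the cost window is equally explicit.

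The cost is a few sentences and no new data collection. Two limits should be stated with the result. The baseline questionnaire is completed at screening, at an interval before surgery that the documents do not give, so placing it at surgery is an assumption. With no measurement between baseline and 3 months, the straight line may also miss a deeper early post-operative dip.
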